3.12.3 EpiTrack Junior

According to the protocol, in the calculation of the EpiTrack Junior score the same age correction, using the age at EV, will be applied at all visits even if a participant changes age category during the study. However, the EpiTrack Junior author has confirmed that in a LTFU study the age correction for each participant should be consistent with the age correction used in the original study. The SAP has therefore been updated to state that the total adjusted EpiTrack Junior score will be obtained from the total unadjusted EpiTrack Junior score by applying an age correction using the participant age at N01269 Baseline for all assessments.

3.13 Definitions of study specific derived variables

3.13.1 Seizures

Each seizure code in the EEG and Seizure Classification eCRFs will be assigned to exactly 1 of the following codes based on the 1981 International League Against Epilepsy (ILAE) classification: IA+IB, IC, IIA (Absence), IIB, IIC, IID, IIE, IIF or III.

3.13.1.1 Non-absence seizures

All non-absence seizures will be categorized into 1 of 3 types:

- Partial onset seizures: “POS”
- Tonic-clonic seizures: “Tonic-clonic”
- All other type 2 or 3 seizures: “All other type 2 and 3 seizures”

The following ILAE categories will contribute to the above categories:

- POS: IA, IB, IC
- Tonic-clonic: IIE
- All other type 2 and 3 seizures: IIB, IIC, IID, IIF, III

3.13.2 Absence seizure freedom during the 1-hour EEG (including dropouts)

The endpoint of absence seizure freedom on 1-hour EEG with no concomitant use of any AEDs, including benzodiazepines, within 4 days prior to or during the EEG will be assessed at each scheduled EEG visit up to and including the Month 24 YEV (or FV, if applicable) or EDV.

At each timepoint, a study participant is defined as absence seizure free if they meet all the following criteria:

1. 1-hour EEG was conducted on the study participant
2. Quality of 1-hour EEG while awake deemed sufficient for analysis
3. No absence seizure identified while awake on 1-hour EEG
4. No concomitant use of any AEDs, including benzodiazepines, on the day of initiating and during the 1-hour EEG or the 4 study days prior to it

Specific algorithmic rules for each of the above criteria are defined as follows:

Criterion 1: A study participant is defined as receiving the 1-hour EEG if there is a record that this test was conducted in the eCRF.

Criterion 2: The EEG is deemed of sufficient quality if at least 30 minutes of readable EEG while awake is recorded, as reported on the EEG eCRF.

Criterion 3: 1-hour EEG with no absence seizures recorded on the EEG eCRF (ILAE code IIA).

Criterion 4: No records of any concomitant AED, including benzodiazepines usage on the Concomitant Medications eCRF on the day of initiating the 1-hour EEG, or the 4 days prior to it.

Note that Criteria 2, 3 and 4 can only be assessed if Criterion 1 is met.

At each timepoint, if the study participant does not meet all the criteria for absence seizure freedom they will be regarded as not absence seizure free. If a participant discontinues the study early, prior to Month 24, they will be imputed as not absence seizure free for all subsequent scheduled visits after the EDV until Month 24. If a participant has a FV prior to the Month 24 assessment visit, they will not be included in any summaries for the scheduled visits following the FV.

In the event where multiple scheduled locally read 1-hour EEGs are recorded at the same timepoint, only the first EEG will be used for analysis, regardless of the quality of this EEG. The later EEGs will be considered as exploratory and listed only.

3.13.3 Absence seizure freedom during the 1-hour EEG (excluding dropouts)

The endpoint of absence seizure freedom based on 1-hour EEG with no concomitant use of any AEDs, including benzodiazepines, within 4 days prior to or during the EEG excluding dropouts will be assessed at each scheduled EEG visit up to and including the Month 24 YEV (or FV, if applicable). If a study participant misses a scheduled EEG and does not discontinue the study within the protocol defined visit window for that EEG, they will be imputed as not absence seizure free at the visit. If a study participant discontinues the study early, they will not be included in the analysis for any subsequent visits. If a participant has a FV prior to the Month 24 assessment visit, they will not be included in any summaries for the scheduled visits following the FV.

The endpoint of absence seizure freedom will be derived in the same way as described in [Section 3.13.2](#).

At each timepoint, if the study participant does not meet all the criteria for absence seizure freedom they will be regarded as not absence seizure free.

In the event where multiple scheduled locally read 1-hour EEGs are recorded at the same timepoint, only the first EEG will be used for analysis, regardless of the quality of this EEG. The later EEGs will be considered as exploratory and listed only.

3.13.4 Absence seizure freedom based on diary (including dropouts)

The endpoint of absence seizure freedom based on diary will be assessed at 3-month time intervals within the Evaluation Period, as defined in [Table 3-3](#), and over the entire Evaluation Period. The Evaluation Period may include any additional diary entries collected from the end of the Months 22 to 24 period up to the Month 24 YEV where the Evaluation Period is truncated for participants who reach the Month 24 YEV.

In each 3-month period (or Evaluation Period), a study participant is defined as absence seizure free if they meet all the following criteria:

1. The study participant completed their seizure diary on at least 80% of days within the relevant period. Seizure diary is defined as completed if “Diary completed” is answered “Yes” for each applicable day in the period. If “Diary completed” is answered “No” or the diary record is missing it will be defined as not completed for that day.
2. No absence seizures are reported in the seizure diaries in the relevant period
3. No concomitant use of any AEDs, including benzodiazepines during the relevant period

Specific algorithmic rules for each of the above criteria are defined as follows:

Criterion 1: Seizure diary data is reported on the Seizure Classification eCRF for at least 80% of the days within the relevant period

Criterion 2: No diary records on the Seizure Classification eCRF within the relevant period are reported with answer “Yes” to the question “Did Any Absence Seizures occur?”

Criterion 3: No records of any concomitant AED, including benzodiazepines, usage on the Concomitant Medications eCRF within the relevant period

Note that Criterion 2 and 3 will only be assessed if Criterion 1 is met. In each 3-month period (or Evaluation Period), if the study participant does not meet all the criteria for absence seizure freedom they will be regarded as not absence seizure free.

If a study participant discontinues the study during a 3-month period then Criterion 1 will be checked based on the full 3-month period and if met, the participant will be assessed for absence seizure freedom in the period of discontinuation. If Criterion 1 is not met, absence seizure freedom status will be imputed as not absence seizure free for the period of discontinuation and all subsequent 3-month periods, ending at Months 22 to 24. Study participants who discontinue the study early will still be included in the analysis conducted on the Evaluation Period.

If a study participant has a FV during a 3-month period then Criterion 1 will be checked based on the full 3-month period and if met, the participant will be assessed for absence seizure freedom in the period of the FV. If Criterion 1 is not met, the participant will not be included in the summary for that period and all subsequent 3-month periods, ending at Months 22 to 24. Study participants who have a FV prior to the scheduled Month 24 YEV will still be included in the analysis conducted on the Evaluation Period.

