To investigate long-term efficacy of BRV in pediatric study participants with CAE or JAE	
 Absence seizure freedom based on diary over the Evaluation Period truncated at Month 24 and by each applicable 3-month time interval up to Months 22-24 
Estimand
 
 Population: the study participant population as defined in the protocol-specified inclusion/exclusion criteria reflecting the target patient population. Study participant-level outcome: seizure freedom response on diary over the Evaluation Period truncated at Month 24 and by each applicable 3-month time interval up to Months 22-24. Intercurrent event handling: The intercurrent event of concomitant use of any AED, including benzodiazepines, during each applicable 3-month period is handled in the definition of the participant-level variable implementing a composite strategy in which receiving any concomitant AED, including benzodiazepines, in the 3-month period or during the visit is counted as nonresponse (ie, considered as having absence seizures). The intercurrent event of diary completion during each applicable period is handled in the definition of the participant-level variable implementing a composite strategy in which completing less than 80% of diaries during the 3-month period is counted as nonresponse (ie, considered as having absence seizures). Population-level summary measure: percentage of study participants free from clinical absence seizures.
Secondary objective	Other endpoints
To investigate long-term efficacy of BRV in pediatric study participants with CAE or JAE	
 Consecutive absence seizure freedom in 6-month periods based on EEG up to Month 24 Consecutive absence seizure freedom in 6-month periods based on diary up to Month 24

AED=antiepileptic drug, BRV=brivaracetam, CAE=childhood absence epilepsy, EEG=electroencephalogram, JAE=juvenile absence epilepsy, SAE=serious adverse event, TEAE=treatment-emergent adverse event

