3.13.5 Absence seizure freedom based on diary (excluding dropouts)

The endpoint of absence seizure freedom based on diary will be assessed at 3-month time intervals within the Evaluation Period, as defined in [Table 3-3](#), and over the entire Evaluation Period. The Evaluation Period may include any additional diary entries collected from the end of the 3-month Months 22 to 24 period up to the Month 24 YEV where the Evaluation Period is truncated for participants who reach the Month 24 YEV.

The derivation will be the same as [Section 3.13.4](#) apart from if a study participant discontinues or completes the study during a 3-month period then Criterion 1 will be checked and if met, the participant will be assessed for absence seizure freedom in the period of discontinuation. If they do not meet Criterion 1 during the period of study discontinuation the study participant will not be included in the analysis for that period. Additionally, they will not be included in the analysis of any period subsequent to that of study discontinuation or completion. If a study participant discontinues the study at any time before the scheduled Month 24 YEV, they will not be included in the analysis conducted on the Evaluation Period. However, if a study participant has a FV prior to the scheduled Month 24 YEV, they will be included in the analysis conducted on the Evaluation Period.

3.13.6 Absence seizure freedom based on diary with modified criterion based on seizure diary completion (including dropouts)

The endpoint of absence seizure freedom based on diary with modified criterion based on seizure diary completion (including dropouts) will be derived in the same way as the endpoint defined in [Section 3.13.4](#), however Criterion 1 will be updated to require a minimum of 50% of days of seizure diary completion within the relevant period.

3.13.7 Absence seizure freedom based on diary with modified criterion based on seizure diary completion (excluding dropouts)

The endpoint of absence seizure freedom based on diary with modified criterion based on seizure diary completion (excluding dropouts) will be assessed at 3-month time intervals within the Evaluation Period, as defined in [Table 3-3](#), and over the entire Evaluation Period. The Evaluation Period may include any additional diary entries collected from the end of the Months 22 to 24 period up to the Month 24 YEV where the Evaluation Period is truncated for participants who reach the Month 24 YEV.

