3.13.9 Consecutive absence seizure freedom based on diary

The endpoint of consecutive absence seizure freedom based on diary is defined, per 6-month period within the Evaluation Period, as having no absence seizures during that period. This will be assessed at 6-month time intervals within the Evaluation Period, as defined in [Table 3-4](#), and over the entire Evaluation Period. Consecutive absence seizure freedom for the Evaluation Period is defined as having no absence seizures for the entire Evaluation Period which also includes any additional diary entries collected from the end of the 6-month Months 19 to 24 period up to the Month 24 YEV where this is truncated for participants who reach the Month 24 YEV.

The endpoint of cumulative consecutive absence seizure freedom is defined, per 6-month period within the Evaluation Period, as having no absence seizures during that period and all preceding periods (where applicable). This will be assessed at 6-month time intervals within the Evaluation Period, as defined in [Table 3-4](#).

The derivation will be the same as that outlined in [Section 3.13.4](#), except without the consideration of concomitant AEDs or benzodiazepines usage.

In each 6-month period (or Evaluation Period), a study participant is defined as absence seizure free if they meet all the following criteria:

1. The study participant completed their seizure diary on at least 80% of days within the relevant period. Seizure diary is defined as completed if “Diary completed” is answered “Yes” for each applicable day in the period. If “Diary completed” is answered “No” or the diary record is missing it will be defined as not completed for that day.
2. No absence seizures are reported in the seizure diaries in the relevant period

Specific algorithmic rules for each of the above criteria are defined as follows:

Criterion 1: Seizure diary data is reported on the Seizure Classification eCRF for at least 80% of the days within the relevant period

Criterion 2: No diary records on the Seizure Classification eCRF within the 6-month period are reported with answer “Yes” to the question “Did Any Absence Seizures occur?”

Note that Criterion 2 will only be assessed if Criterion 1 is met. In each 6-month period (or Evaluation Period), if the study participant does not meet all the criteria for absence seizure freedom they will be regarded as not absence seizure free.

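### The Evaluation Period diary result applies the 80% completion rule once to all days pooled, so a participant can count as seizure free over 24 months while failing 3-month intervals inside it, and SAP 3.12 declares no change from the estimand

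*SAP*

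**What the plan says.** SAP Section 3.13.4 uses one list of criteria for two kinds of period: "In each 3-month period (or Evaluation Period), a study participant is defined as absence seizure free if they meet all the following criteria". The criteria are:

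- Criterion 1: "The study participant completed their seizure diary on at least 80% of days within the relevant period". On blank days: "If “Diary completed” is answered “No” or the diary record is missing it will be defined as not completed for that day".
- Criterion 2: "No absence seizures are reported in the seizure diaries in the relevant period".
- Criterion 3: "No concomitant use of any AEDs, including benzodiazepines during the relevant period".

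Section 3.13.5 (excluding dropouts) takes over this derivation. Nothing in 3.13.4, 3.13.5, 8.1.3 or 8.1.4 limits the length of a gap or carries a failed 3-month interval into the Evaluation Period result.

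The estimand in SAP Table 2-2, which matches protocol Section 3, covers the Evaluation Period and the 3-month intervals together. Its diary rule opens by referring to completion in each period that applies, and then says that "completing less than 80% of diaries during the 3-month period is counted as nonresponse".

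The sensitivity versions (3.13.6 and 3.13.7) keep the structure with a lower bar: "Criterion 1 will be updated to require a minimum of 50% of days of seizure diary completion within the relevant period". Section 3.13.9 applies the 80% rule to 6-month periods and to the Evaluation Period ("Seizure diary data is reported on the Seizure Classification eCRF for at least 80% of the days within the relevant period"). It also defines a cumulative version in which the first failed 6-month period carries forward.

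Section 3.12 lists three changes from the protocol: concomitant antiepileptic drugs (AEDs), truncation at Month 24, and the EpiTrack age correction. Diary completion is not among them.

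**The concern.** The Evaluation Period result is the plan's diary-based measure of sustained freedom over about two years. Someone free of seizures throughout must be free in every interval inside. Under the pooled rule this need not hold. Criterion 2 looks only at recorded entries, so blank days cannot fail it. Criterion 1, which is meant to guard against blank days, is diluted by the other 21 months.

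Two things are at stake. First, the estimand's operative clause names the 3-month period, so the derivation may not deliver the stated estimand for this outcome. Second, the effect runs one way: pooling can turn a participant with a failed interval into a whole-period responder. In the including-dropouts table, interval and whole-period percentages share the Safety Set as denominator (SAP 8.1.3), so the 24-month percentage could exceed that of an interval within it. In the excluding-dropouts table (8.1.4), the same participant leaves the denominator of the failed intervals but still counts as seizure free for the whole period.

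**Working it through.** **Inputs.** Thresholds of 80% and 50% (SAP 3.13.4, 3.13.6). Intervals of 90 days, with Months 19-21 as Days 541-630 and Months 22-24 as Days 631-720 (Table 3-3). Month 24 visit on Day 731 (Section 3.3.3, Table 3-5). Visit window of ±7 days (protocol Table 1-1). I assume the first dose is on the day of the Entry Visit, as SAP 3.3.2 expects, so the truncated Evaluation Period is Days 1-731.

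**Plan's own figure.** 24 × 365.25/12 = 730.5, which rounds to the stated 731.

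**Largest gap at 80%.** 0.80 × 731 = 584.8, so 585 days are needed and 731 − 585 = 146 may be blank. 585/731 = 80.03% passes; 584/731 = 79.89% fails.

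**Blank from Day 586 to Day 731:**

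| Period | Diary days | Criterion 1 |
|---|---|---|
| Six intervals, Days 1-540 | 90/90 each | met |
| Months 19-21 | 45/90 = 50% | not met |
| Months 22-24 | 0/90 | not met |
| Evaluation Period | 585/731 = 80.03% | met |

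With no recorded absence seizure and no AED, this participant is seizure free over the Evaluation Period and not seizure free in two of its eight intervals.

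**Visit window.** A visit on Day 724 needs 580 days and allows 144 blank; Day 738 needs 591 and allows 147. The same two intervals fail (40/90 and 0/90; 51/90 and 0/90).

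**A less extreme case.** One missing 90-day diary gives (731 − 90)/731 = 641/731 = 87.7% overall and 0/90 in its own interval.

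**Section 3.13.9.** The 146-day participant has 45/180 = 25% in Months 19-24. The cumulative analysis calls them not seizure free; the Evaluation Period result in the same section calls them seizure free.

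**50% version.** 0.50 × 731 = 365.5, so 366 days suffice. With Days 367-731 blank, Months 13-15 has 6/90 and the next three intervals 0/90: four of eight fail and the whole period passes.

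**Under the fix.** Pooling Days 721-731 with Months 22-24 gives 101 days. 0.80 × 101 = 80.8, so 81 are needed and 20 may be blank. The 146-day participant then has 45/90 and 0/101 and fails. The longest gap at the end falls from 146 to 20 days. The longest gap anywhere is 18 + 20 = 38 days, across the boundary at Day 630.

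**The case against.** The best defence is textual. The estimand's clause opens with each applicable period, its outcome includes the Evaluation Period, and applying 80% to whichever period is being analysed is a fair reading of those words. That stands as ambiguity. It does not settle the matter, because the clause that defines nonresponse names the 3-month period.

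Second, the output shows part of the problem. The 3-month rows and the numbers meeting Criterion 1 appear in the same summary, daily diary completion is listed (SAP Section 8), and the cumulative 6-month analysis would catch the 146-day example. The answer is only partial: that analysis ignores AEDs, stops at Day 720, and does not alter the whole-period percentage.

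Third, the 146-day case is a limit. It needs complete diaries to Day 585, none afterwards, and continued attendance. Protocol Table 1-2 has diaries retrieved at each 3-monthly visit, protocol 7.3.2 has them discussed for completeness, and the Month 21 visit (Day 639) falls inside the gap. This stands. A reader might infer that such gaps are common, or that diaries are typically abandoned late, but the documents give no completion data.

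Fourth, a crude remedy would do harm. An 80% test on the days after Day 720 alone would rest on 4 to 18 days: three missed of 11 (8/11 = 73%) would fail a participant for 24 months. A 90-day denominator in the interval of an early Final Visit would make completers nonresponders. Both points stand and shape the fix.

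**Conclusion.** The concern holds. The pooled criterion lets a participant be seizure free over the Evaluation Period while failing up to two of eight intervals through one terminal gap of 146 days (144 to 147 across the visit window), or one interval through a single missing diary. This assumes the participant reaches the Month 24 visit, with no recorded absence seizure and no AED in the whole period. The derivation does not implement the 3-month wording for this outcome, and the SAP does not declare that.

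Three stronger readings are not supported. The SAP cannot be said to contradict the estimand outright, given the ambiguous opening words. The 365-day gap belongs to a labelled, deliberately lenient sensitivity analysis and is not what the secondary endpoint itself would claim; that analysis does, however, relax the same rule and so cannot reveal this problem. And no size can be put on the overstatement, because the number of participants affected is unknown. The endpoint is secondary and descriptive with no hypothesis testing (protocol 9.2), so this is a correction that should be made, not a threat to the primary safety objective.

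**What to change.** In SAP 3.13.4 and 3.13.5, count a participant as absence seizure free over the Evaluation Period only if Criterion 1 is met in every 3-month interval entered, with Criteria 2 and 3 still applied to the whole period. Specify:

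- Days after Day 720, up to the Month 24 visit, are pooled with Months 22-24 and not tested alone.
- For the Evaluation Period result, the interval containing an early Final Visit or Early Discontinuation Visit is assessed over the days up to that visit. A stub of a few days has the same small-denominator problem as the days after Day 720, so state when it is pooled with the preceding interval.
- The same construction applies at 50% in 3.13.6 and 3.13.7, and at 80% to the Evaluation Period result in 3.13.9.

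State in Table 2-2 which period the diary rule refers to. Keep the pooled version as a supplementary row, so that the difference shows how many participants are affected.

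The cost is modest: a few sentences per section, using interval completion that is largely derived already. The whole-period percentage can only stay the same or fall. A participant with 19 or more blank days in one 90-day interval (71/90 = 78.9%) becomes a nonresponder even if otherwise complete (712/731 = 97.4%); in the pooled 101-day interval the figure is 21. Agreement will not be perfect. With all 11 tail days complete, 70 or 71 of 90 days in Months 22-24 would pass the pooled interval and fail its own row. Participants with an early Final Visit also still leave later rows while staying in the whole-period result.
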